#### 7.2 Definitions

#### 7.2.1 Adverse Event

#### **Adverse Event Definition**

An adverse event (AE) is any untoward medical occurrence in a subject participating in an investigational study or protocol regardless of causality assessment. An adverse event can be an unfavorable and unintended sign (including an abnormal laboratory finding), symptom, syndrome or disease associated with or occurring during the use of an investigational product whether or not considered related to the investigational product.

Diagnostic and therapeutic non-invasive and invasive (i.e., surgical) procedures will not be reported as adverse events. However, the medical condition for which the procedure was performed must be reported if it meets the definition of an adverse event unless it is a pre-existing (prior to protocol treatment) condition.

#### 7.2.2 Serious Adverse Event

An adverse event is considered "serious" if, in the view of the investigator, it results in any of the following outcomes:

#### Death

If death results from (progression of) the disease, the disease should be reported as event (SAE) itself.

- A life-threatening adverse event An adverse even is considered 'life-threatening' if, in the view of either the investigator, its occurrence places the subject at immediate risk of death. It does not include an adverse event that, had it occurred in a more severe form, might have caused death.
- Inpatient hospitalization or prolongation of existing hospitalization for > 24 hours.
- A persistent or significant incapacity or substantial disruption of the ability to conduct normal life functions
- A congenital anomaly/birth defect
- Important medical event

Any event that may not result in death, be life-threatening, or require hospitalization may be considered serious when, based upon appropriate medical judgment, it may jeopardize the subject and may require medical or surgical intervention to prevent one of the outcomes listed in this definition of "Serious Adverse Event." Examples of such medical events include allergic bronchospasm requiring intensive treatment in an emergency room or at home; convulsions that do not result in inpatient hospitalization or the development of drug dependency or drug abuse.

Previously planned (prior to signing the informed consent form) surgeries should not be reported as SAEs unless the underlying medical condition has worsened during the course of the study. Preplanned hospitalizations or procedures for preexisting conditions that are already recorded in the subject's medical history at the time of study enrollment should not be considered SAEs. Hospitalization or prolongation of hospitalization without a precipitating clinical AE (for example, for the administration of study therapy or other protocol-required procedure) should not be considered SAEs. However, if the preexisting condition worsened during the course of the study, it should be reported as an SAE.

#### 7.2.3 Expected Adverse Events

An adverse event (AE) is considered "expected" if:

- For approved and marketed drugs or devices, those adverse events are described in the approved Package Insert (Label).
- For investigational new drugs or devices, those adverse events are described in the FDA Investigator's Brochure.
- In clinical research studies, information on expected adverse events is also summarized in the protocol and in the consent document. See section 8.1 for the list of expected adverse events related to the drug under study.

# 7.2.4 Unexpected Adverse Event

An adverse event (AE) is considered "unexpected" if it is not described in the Package Insert, Investigator's Brochure, in published medical literature, in the protocol, or in the informed consent document.

#### 7.3 Adverse Event Characteristics

# 7.3.1 Terms and Grading

The severity or grade of an adverse event may be measured using the following definitions:

**Mild:** Noticeable to the subject, but does not interfere with subject's expected daily activities, usually does not require additional therapy or intervention, dose reduction, or discontinuation of the study.

**Moderate:** Interferes with the subject's expected daily activities, may require some additional therapy or intervention but does not require discontinuation of the study.

**Severe:** Extremely limits the subject's daily activities and may require discontinuation of study therapy, and/or additional treatment or intervention to resolve.

#### 7.3.2 Attribution of the AE

The investigator or co-investigator is responsible for assignment of attribution.

Definite – The AE is clearly related to the study treatment/intervention.

Probable – The AE is likely related to the study treatment/intervention.

Possible – The AE may be related to the study treatment/intervention.

Unlikely – The AE is doubtfully related to the study

treatment/intervention.

Unrelated – The AE is clearly NOT related to the study treatment/intervention.

# 7.4 Serious Adverse Event Reporting Guidelines

- 7.4.1 The Principal Investigator must be notified within 7 business day of study team's knowledge of any event meeting the criteria and definition of a serious adverse event, regardless of attribution, occurring during the study or within 30 days of the last administration of the study related treatment/intervention.
- 7.4.2 The investigator must report all events meeting the criteria and definition of a serious adverse event as per the local IRB reporting requirements.

#### 7.5 Reporting of Unanticipated Problems

Unanticipated problem: Per FDA Procedural Guidance for Clinical Investigators, Sponsors, and IRBs (January 2009), an unanticipated problem is defined as a serious problem that has implications for the conduct of the study (requiring a significant and usually safety-related, change in the protocol (such as revising inclusion/exclusion criteria or including a new monitoring requirement), informed consent or investigator's brochure).

Upon becoming aware of any incident, experience, or outcome (not related to an adverse event) that may represent an unanticipated problem, the investigator should assess whether the incident, experience, or outcome represents an unanticipated problem. The incident, experience, or outcomes is considered unanticipated if it meets all of the following criteria:

- 1. Unexpected (in terms of nature, severity, or frequency);
- 2. Related or possibly related to participation in the research; and
- 3. Suggests that the research places subjects or others at a greater risk of harm than was previously known or recognized.

Unanticipated problem Reporting: Per 21 CFR 312.66, 312.53 (c)(1)(vii), and 56.108(b)(1), should an Unanticipated problem occur during the investigation, the investigator will promptly report all unanticipated problems involving risks to human subjects or others to the IRB.

# 8.0 DRUG INFORMATION

#### 8.1 Tranexamic Acid (TXA)

See following link to drug insert for more details: https://dailymed.nlm.nih.gov/dailymed/fda/fdaDrugXsl.cfm?setid=a30cd382-4e2a-428d-a6d1-a530f4d230c1&type=display

- Manufacturer: Apollo Pharmaceuticals USA Inc.
- Route of administration: The drug use for this study is approved for IV use. The drug will be used topically for this study.
- Mode of action: TXA inhibits of the conversion of plasminogen to plasmin which then prevents the breakdown of fibrin clots.
- Pharmacokinetics:
  - Distribution: The initial volume of distribution is about 9-12 liters. The plasma protein binding of tranexamic acid is about 3% at therapeutic plasma levels and seems to be fully accounted for by its binding to plasminogen. Tranexamic acid does not bin to serum albumin.

- Elimination: After an IV dose of 1 g of TXA, the plasma concentration time curve shows a triexponential decay with half-life of about 2 hours for the terminal elimination phase.
- Excretion: Urinary excretion is the main route elimination via glomerular filtration. Overall renal clearance is equal to overall plasma clearance (110-116 mL/min), and more than 95% of the dose is excreted in the urine as unchanged drug. Excretion of tranexamic acid is about 90% at 24 hours after IV administration of 10 mg/kg body weight.
- Contraindications: Subarachnoid hemorrhage, active intravascular clotting
- Potential Side Effects: Thromboembolic events, seizures, hypersensitivity reactions, visual disturbances, dizziness
- Drug Interactions: No studies of interactions beteen tranexamic acid and other drugs have been conducted.
- Storage and Stability: Store at 20 C to 25 C
- Preparation Dispensing, and Labeling:
   The TXA solution will be prepared by the University of Michigan OR pharmacy.
   The drug will be prepared according to the following table.

	Concentration	Volume
Tranexamic acid	100 mg/ml	40 ml
Sodium chloride	0.9%	110 ml
Final	4000 mg/150 ml	150 ml

The prepared solution is to be used within 6 hours on the same day of the preparation.

- Availability: Commercially available
- Return and Retention of Study Drug: The remaining/expired/used or returned drug is to be destroyed on site. The drug destruction is according to the institution standard operating procedure for drug destruction
- Drug Accountability: The University of Michigan OR Pharmacy will be providing the drug and managing the drug supply according to the institution stanard operating procedures.

# 9.0 STATISTICAL CONSIDERATIONS

Sample size calculation was performed for a 50% reduction in hematoma requiring operative intervention or aspiration. The study would have 80 percent power to detect the expected 50 percent risk reduction (assuming  $\alpha = 0.05$ ,  $\beta = 0.20$ , n1:n2 of 1:1) if 250 patients are enrolled in each cohort.

Descriptive statistics of demographics and clinical characteristic of patients will be calculated. The descriptive statistics will be compared between the two treatment arms to assess any obvious imbalance in risk factors, despite the use of randomization.

A primary goal of the study is to evaluate the rate of hematoma requiring operation washout or aspiration in patients who receive topical TXA versus patients who do not receive topical TXA intraoperatively during breast reduction or gender-affirming mastectomy. This data will be presented as frequency counts and percentages and analyzed using Fisher's exact test. A value of p < 0.05 is considered statistically significant.

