	presented as frequency counts and percentages and analyzed using Fisher's exact test.				
	PISHEL S CARCILLEST.				

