# STUDY SCHEMA

#### 1.0 BACKGROUND AND RATIONALE

Reduction mammoplasty and gender-affirming mastectomy are two common plastic surgery operations that are generally performed in relatively healthy patients in the outpatient setting. Although these procedures are relatively safe and have a low complication profile, reoperations can occur due to hematomas. The reported incidences of hematoma following reduction mammoplasty and gender-affirming mastectomy are around 3%-9% and 5%-10%, respectively. Most clinically significant hematoma will require operative washout or aspiration. If left untreated, hematomas can lead to nipple necrosis and skin flap compromise which can negatively impact patient satisfaction and aesthetic outcome.

Tranexamic acid (TXA) has emerged over the past decade as an adjunctive pharmacologic agent to reduce intraoperative blood loss and prevent post-operative bleeding. Its mechanism involves inhibition of the conversion of plasminogen to plasmin which then prevents the breakdown of fibrin clots. The efficacy of tranexamic acid has been demonstrated in cardiac surgery, orthopedic surgery, spine surgery. However, the use of tranexamic acid has not been routinely adapted into plastic surgery practice. There have been some studies assessing the use of tranexamic acid in plastic surgery procedures, including facial aesthetic surgery, craniofacial surgery, and breast reconstruction. In addition, the route of administration can include intravenous, oral, or topical. Some believe that the topical use of tranexamic acid provides a direct hemostatic benefit during surgery while decreasing systemic absorption. The concentration of topical tranexamic acid has been reported from 1.5% to 3% in orthopedic surgery and aesthetic surgery. Currently, the data suggests that tranexamic acid decreases intraoperative blood loss, postoperative bruising, and surgical drain output. However, there is a paucity of randomized prospective data on the efficacy of topical tranexamic acid in reducing clinically significant reoperative hematomas in breast surgeries.

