# 2.0 STUDY DESIGN, OBJECTIVES AND OUTCOME MEASURES

#### 2.1 Primary Objectives

To evaluate the safety and efficacy of topical tranexamic acid use in preventing hematomas in routine breast plastic surgery operations

Primary Outcome Measure:

1. Incidence of hematoma requiring operative intervention

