#### 4.2 Randomization

Patients will be randomized in a 1:1 ratio to either the TXA arm or the non-TXA arm. Randomization will occur pre-operatively in REDCap, the study's data management system.

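### Should the primary analysis replace Fisher's exact test with a more powerful exact unconditional test?

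*Combined protocol and SAP*

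**What the plan says.** Section 9.0 compares the arms on hematoma needing washout or aspiration. The counts and percentages are to be "analyzed using Fisher's exact test. A value of p < 0.05 is considered statistically significant". The synopsis names the same test for the primary and secondary outcomes: "presented as frequency counts and percentages and analyzed using Fisher's exact test". The two places agree.

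Four other statements bear on the choice:

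- Section 4.2: "Patients will be randomized in a 1:1 ratio to either the TXA arm or the non-TXA arm". No blocking or stratification is described.
- Section 1.0 puts hematoma after breast reduction and after gender-affirming mastectomy at "around 3%-9% and 5%-10%, respectively".
- Section 2.1 words the primary outcome as "Incidence of hematoma requiring operative intervention", while Sections 1.0 and 9.0 also count aspiration. Either is narrower than any hematoma.
- Section 9.0, for 250 patients per arm: "The study would have 80 percent power to detect the expected 50 percent risk reduction".

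The plan states neither sidedness nor a control rate.

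**The concern.** Fisher's test conditions on the total number of events, which this design does not fix in advance. With sparse events the conditional distribution is coarse, so the attained error falls below 5% and power is lost. An unconditional exact test, which treats the arms as two binomials and controls the maximum error over the unknown common rate, uses more of the 5%.

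What is at stake is a result near the threshold. At 250/250 with 9 versus 20 events, Fisher gives p = 0.054 and the pooled-z exact test gives p = 0.038. The same patients and the same nominal alpha lead to opposite conclusions, and naming another test would need no more patients.

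**Working it through.** **Inputs.** From the plan: 500 patients, 1:1 allocation, alpha 0.05, a 50% reduction, and background rates of 3%-10%. Assumed, because the plan is silent: two-sided testing, those background rates as control rates, complete outcome data, and simple randomisation where results are averaged over splits.

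**The plan's power figure first.** Power = Φ{[d√n − 1.96√(2p̄(1−p̄))] / √(p1(1−p1)+p2(1−p2))}. For 10% versus 5% with n = 250: d√n = 0.05 × 15.811 = 0.7906; 1.96 × √(2 × 0.075 × 0.925) = 0.7301; denominator √(0.0900 + 0.0475) = 0.3708. Power = Φ(0.163) = 56.5%. The stated 80% is not reproduced at 3%-10%; it needs a control rate of about 16.4%. This shortfall exists whichever test is used.

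**Error and power at exactly 250/250.** Every 2×2 table is enumerated. Fisher rejects at p < 0.05 (tables ordered by probability). Pooled-z rejects at |z| ≥ 1.981, the smallest cut-off whose maximum error over the common rate is at most 5% (attained 4.98%).

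| Control rate | Fisher error | Fisher power | Pooled-z power | Gain (points) |
|---|---|---|---|---|
| 3% | 2.57% | 12.1% | 17.9% | 5.8 |
| 5% | 3.17% | 23.8% | 30.5% | 6.6 |
| 7% | 3.44% | 35.1% | 41.7% | 6.6 |
| 9% | 3.54% | 46.1% | 51.9% | 5.8 |
| 10% | 3.55% | 51.2% | 56.4% | 5.2 |

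**Averaged over splits.** Under simple randomisation exactly 250/250 has probability 3.6%. With Binomial(500, 0.5) weights, Fisher's error is 3.50%-4.18% (largest at any single split 4.29%). Power at 3/5/7/9/10% is 15.2/26.8/38.0/48.6/53.6% for Fisher and 19.1/30.4/41.3/51.6/56.4% for pooled-z, a gain of 2.8-3.8 points. By split the gain runs from about 0 to 6.7 points. With 251 TXA and 249 control patients and a 7% control rate, power is 40.96% versus 40.99%.

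**Error given the event total.** If TXA changes no patient's outcome, the event total is the same whatever the allocation. The number falling in one arm is then hypergeometric. At 250/250 the pooled-z rule rejects with these probabilities:

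| Total events | Pooled-z | Fisher |
|---|---|---|
| 8 | 6.8% | 0.7% |
| 16 | 7.2% | 1.9% |
| 21 | 7.2% | 2.4% |
| 29 | 5.4% | 2.0% |
| 33 | 7.0% | 2.9% |

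For common rates of 2.25%-7.5%, the chance of a total at which pooled-z exceeds 5% is about 35%-41%. The 9-versus-20 example is one of these. Pooled z = (11/250) / √(0.058 × 0.942 × 2/250) = 0.0440/0.0209 = 2.10, above 1.981, so the rule rejects. But of 29 events the chance of 9 or fewer in a given arm is 0.0270, and 2 × 0.0270 = 0.054. The rule is therefore rejecting at a conditional level of 5.4%, which is exactly Fisher's p-value.

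**If the sample size were corrected.** For 10% versus 5% and 80% power, n = (0.7301 + 0.8416 × 0.3708)² / 0.05² = 1.0422² / 0.0025 = 434.4, so 435 per arm. At 870 patients the average power is 78.9% for Fisher and 80.4% for pooled-z, a gain of 1.5 points; at exactly 435/435 it is 77.1% versus 80.3%.

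**The case for a change.** The best case for switching is that the gain needs no patients and was not negative at any split checked. To match pooled-z at 500 patients, Fisher would need about 530 at a 10% control rate and about 565 at 5%, so the change is worth roughly 30-65 patients in a trial that does not replace subjects. The chance of a table that only Fisher rejects averages at most 0.03%. The direction holds at control rates of 1% and 2% (gains of 3.7 and 4.2 points), with 5% of outcomes missing (2.7-3.7), and with splits within two patients of balance (2.9-4.3).

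These figures stand. What does not stand is the claim that the alternative is equally valid without qualification. That holds in the two-binomial model, where error is averaged over event totals. In a single-centre randomised trial of scheduled patients, the randomisation model is at least as natural. There Fisher is exact given the arm sizes, and the alternative exceeds 5% at many plausible totals.

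The practical cost is also more than a change of name: the ordering statistic must be specified and the software checked. For 9/260 versus 18/240 Fisher gives 0.0497, but pooled-z gives 0.051 and one common two-sided Boschloo routine gives 0.0595. For a single-centre study labelled a feasibility study, a familiar test with guaranteed error control is a reasonable choice.

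**Conclusion.** No change follows. Fisher's conservatism here is real: true error is 2.6%-4.3% under two-sided testing and common rates of 3%-10%. It reflects the choice between conditional and unconditional inference, on which experienced statisticians differ. The plan's choice is valid, prespecified and consistent between Section 9.0 and the synopsis.

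Switching would add 2.8-3.8 points of power on average at 500 patients if randomisation is simple, 5.2-6.6 at exact balance and almost nothing at some neighbouring splits. The average gain falls to about 1.5 points at 435 per arm. The price is a conditional error of up to 7.2% at the totals tabulated for 250/250. A sponsor who prefers the unconditional model could choose it before seeing outcomes by arm, but nothing in the plan requires it.

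Two neighbouring matters do not alter this. A risk difference with a confidence interval can be reported beside Fisher's p-value without replacing the test. The 80% power statement is wrong at the plan's own background rates under either test, and has to be dealt with on its own.

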#### 10.0 DATA AND SAFETY MONITORING

The study team is required to meet at least quarterly to discuss matters related to:

- Enrollment rate relative to expectations, characteristics of participants
- Safety of study participants (Serious Adverse Event & Adverse Event reporting)
- Adherence to protocol (protocol deviations)
- Completeness, validity and integrity of study data
- Retention of study participants

# 11.0 REGULATORY

#### 11.1 Institutional Review Board (IRB)

Before implementing this study, the protocol, the proposed informed consent form and other information to be provided to subjects, must be reviewed and approved by a properly constituted IRB. Any amendments to the protocol must be reviewed and approved by the IRB.

#### 11.2 Subject Information and Consent

Study team member will explain to each subject (or legally authorized representative) the nature of the study, its purpose, the procedures involved, the expected duration, the potential risks and benefits involved and any discomfort it may entail. Each subject will be informed that participation in the study is voluntary and that he/she may withdraw from the study at any time and that withdrawal of consent will not affect his/her subsequent medical treatment or relationship with the treating physician.

This informed consent will be given by means of a standard written statement, written in non-technical language. The subject should read and consider the statement before signing and dating it, and should be given a copy of the signed document. If the subject cannot read or sign the documents, oral presentation may be made or signature given by the subject's legally appointed representative, if witnessed by a person not involved in the

study, mentioning that the subject could not read or sign the documents. No subject can enter the study before his/her informed consent has been obtained.

The informed consent form is considered to be part of the protocol, and will be submitted for IRB approval.

